### **2.3.3 Subgroup population**

All subgroup populations are subgroup of enrolled patients.

Immediate alemtuzumab treatment (IAT) subgroup: Patients who received alemtuzumab 12 mg/day from CAMMS323 or CAMMS324 study.

Delayed alemtuzumab treatment (DAT) subgroup: Patients who received SC IFNB-1a from CAMMS323 or CAMMS324 and then received alemtuzumab 12 mg/day in CAMMS03409 study.

## **2.4 STATISTICAL METHODS**

### **2.4.1 Demographics and baseline characteristics**

Continuous data will be summarized using the number of available data, mean, standard deviation (SD), median, minimum and maximum. Categorical and ordinal data will be summarized using the number and percentage of patients.

Parameters will be summarized on the enrolled population analyzed in overall group and by subgroups (IAT vs DAT).

Parameters described in [Section 2.1.1](#) will be summarized b in overall group and by subgroups (IAT vs DAT) using descriptive statistics.

### **2.4.2 Prior or concomitant medications**

The concomitant medications will be presented for the enrolled population. All the medication that taken in TOPAZ study will be considered as concomitant medications.

Medications will be summarized in overall group and by subgroups (IAT vs DAT) according to the WHO-DD dictionary, considering the first digit of the anatomic category (ATC) class (anatomic category) and the first 3 digits of the ATC class (therapeutic category). All ATC codes corresponding to a medication will be summarized, and patients will be counted once in each ATC category (anatomic or therapeutic) linked to the medication. Therefore patients may be counted several time for the same medication.

The tables for concomitant medications will be sorted by decreasing frequency of ATC followed by all other therapeutic classes based on the incidence in the overall group. In case of equal frequency regarding ATCs (anatomic or therapeutic categories and/or generic names), alphabetical order will be used.

In addition, the alternative MS therapies will be summarized separately. Alternative MS medication will be determined based on the anatomic or therapeutic categories and generic name.

### **2.4.3 Extent of investigational medicinal product exposure**

The extent of IMP exposure will be assessed and summarized within safety population ([Section 2.3.1.1](#)).

#### **2.4.4 Analyses of efficacy endpoints**

The efficacy population will be used for all efficacy analyses.

For MRI endpoints, EDSS, questionnaires endpoints, only data collected in TOPAZ study will be used for analysis in addition of baseline information from previous studies. The long-term baseline is defined as the last available assessment prior to first dose of alemtuzumab or SC IFNB-1a administration in prior studies. It will be applied to long-term efficacy analysis.

For relapse endpoints, data from prior studies (CAMMS323, CAMMS324 and CAMMS03409) should be obtained.

The main long-term analysis for efficacy endpoints is IAT versus DAT comparison. The efficacy of immediate alemtuzumab treatment (Subgroup IAT defined in [Section 2.3.3](#)) and delayed alemtuzumab treatment (Subgroup DAT defined in [Section 2.3.3](#)) groups will be compared for relapse related endpoints, EDSS assessment as well as MRI endpoints.

The analysis in reference of long-term baseline in prior studies by total number of alemtuzumab courses (i.e.  $\leq 3$  vs  $> 3$ ) will be summarized as well.

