## **5 STUDY OBJECTIVES**

### **5.1 PRIMARY**

The primary objective is to evaluate long-term safety of alemtuzumab.

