## 2 STATISTICAL AND ANALYTICAL PROCEDURES

### 2.1 ANALYSIS ENDPOINTS

#### 2.1.1 Demographic and baseline characteristics

The TOPAZ baseline value is defined as the available value assessed on or prior to the V01 Selection visit, unless otherwise specified. The last available value in previous studies can be considered as the baseline if they were evaluated within the pre-specified time window. For brain imaging result, if the last non-missing assessment performed within 6 months prior to the V01 selection visit, it can be considered as baseline. For vital sign, physical examination, EDSS and questionnaires, the time window is 3 months.

For efficacy endpoints (EDSS, MRI), the baseline from prior studies will be considered as long-term baseline, which is defined as last available assessment prior to first dose of alemtuzumab or SC IFNB-1a administration.

All baseline safety and efficacy parameters (apart from those listed below) are presented along with the on-treatment summary statistics in the safety and efficacy sections ([Section 2.4.5](#) and [Section 2.4.4](#)).

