##### **2.4.4.1 Analysis of efficacy endpoint(s)**

###### **2.4.4.1.1 Annualized relapse rate (ARR)**

The estimated annualized relapse rate using negative binomial model with robust variance estimation will be presented by year and in overall. The observed total number of relapses is the dependent variable, the log total amount of follow-up time in years for each patient will be the offset variable and analysis group indicator (IAT vs DAT) and geographic region will be the covariates in the model. Both IAT vs DAT comparison and ARR by alemtuzumab courses will be analyzed. The analysis period starts from prior studies (CAMMS323/324) until the end of TOPAZ study. The model will also be stratified by previous clinical study.

The observed annualized relapse rate will be reported as well, which is defined as the total number of relapses divided by the total years of follow-up for each patient.

The ARR will be presented separately for retreated population in overall group.

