#### *2.4.4.1.2 Proportion of Relapse free patients*

The proportion of patients with relapse-free each year from prior studies (CAMMS323/324) until the end of TOPAZ study will be estimated based on Kaplan-Meier methods. The complementary log-log transformation will be used to construct 95% confidence intervals. A Kaplan-Meier graph summarizing the event probability over time will be presented by subgroups (IAT vs DAT) and by alemtuzumab courses. Hazard ratio and corresponding 95% confidence interval will be calculated using Cox proportional hazards (PH) regression with robust variance estimation (6). Covariates for the Cox PH model will include analysis groups and geographic region and prior clinical studies. Inference will be based on the Wald test of the log hazard ratio (estimated regression coefficient from the model). The analysis period starts from prior studies (CAMMS323/324) until the end of TOPAZ study.

The Kaplan-Meier (KM) estimates will be summarized for retreated population separately.

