### **2.5 DATA HANDLING CONVENTIONS**

#### **2.5.1 General convention**

For long-term analysis, the reference date is the date of first alemtuzumab or SC IFNB-1a treatment in prior studies.

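### The by-alemtuzumab-course efficacy summaries start at first alemtuzumab or interferon dose, so about 2 interferon years of each DAT patient count as by-course outcome

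*SAP*

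**What the plan says.** SAP 2.4.4 makes IAT versus DAT the main long-term efficacy comparison and adds a split at ≤3 versus >3 courses: "The analysis in reference of long-term baseline in prior studies by total number of alemtuzumab courses". The same section fixes the baseline: "The long-term baseline is defined as the last available assessment prior to first dose of alemtuzumab or SC IFNB-1a administration in prior studies". SAP 2.1.1 defines it the same way, and SAP 2.5.1 says that for long-term analysis "the reference date is the date of first alemtuzumab or SC IFNB-1a treatment in prior studies".

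The endpoint sections then apply the split:

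- **ARR (2.4.4.1.1).** "Both IAT vs DAT comparison and ARR by alemtuzumab courses will be analyzed". The only period given is this: "The analysis period starts from prior studies (CAMMS323/324) until the end of TOPAZ study".
- **Relapse-free proportion (2.4.4.1.2).** "A Kaplan-Meier graph summarizing the event probability over time will be presented by subgroups (IAT vs DAT) and by alemtuzumab courses". The stated period is the same.
- **EDSS (2.4.4.1.3).** The change-from-baseline model is repeated by course. TOPAZ entry counts as post-baseline, so change runs from the long-term baseline.
- **MRI (2.4.4.1.4 and 2.4.4.1.5).** Similar by-course analyses are planned for lesion counts and for volumes.

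SAP 2.3.3 defines DAT patients as those given SC IFNB-1a in CAMMS323 or CAMMS324 and alemtuzumab only in CAMMS03409. SAP 1.4 gives the prior studies as 2 years. DAT patients belong to the efficacy population, which 2.4.4 uses for all efficacy analyses. No passage limits the by-course summaries to IAT patients or restarts their clock at first alemtuzumab dose.

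**The concern.** The secondary objective served here is the long-term efficacy of alemtuzumab (protocol 5.2). A table headed by number of alemtuzumab courses will be read as describing patients on that many courses. For DAT patients, part of what it reports happened on the comparator. Protocol section 4 says alemtuzumab was established as superior to SC IFNB-1a on clinical and imaging endpoints, so this time is not neutral.

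The first-relapse curve is the most exposed. A DAT patient who relapses on interferon has the event, and leaves the risk set, before receiving any course. If DAT patients are unevenly spread over the two course groups, the interferon time also creates a difference between the groups that owes nothing to alemtuzumab.

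**Working it through.** The documents state no relapse rate, event count or power for this analysis, so there is no planned figure to reproduce. The check traces the time origin (set out above) and then does person-time arithmetic.

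**Inputs from the documents**

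- Prior studies: 2 years (SAP 1.4).
- Extension: at least 4 years (SAP 1.4), up to 60 months (protocol section 4).
- TOPAZ: 5 years plus a 6-month window (protocol 6.2).

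**Assumptions, because the documents are silent**

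- Constant relapse rates: r_A = 0.2 per year on alemtuzumab, r_I = 0.3 to 0.5 per year on interferon.
- Poisson relapses, and the same alemtuzumab rate in both course groups.
- DAT share 50% in the ≤3 group and 30% in the >3 group.
- Complete follow-up.

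**Step 1: interferon share of DAT follow-up.** Shortest full course: 2/(2 + 4 + 5) = 2/11 = 18%. Longest: 2/(2 + 5 + 5.5) = 2/12.5 = 16%. A patient with less TOPAZ time has a larger share; with 1 TOPAZ year it is 2/7 = 29%.

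**Step 2: DAT ARR as planned.** (2·r_I + (T − 2)·r_A)/T, compared with r_A = 0.2 from first alemtuzumab dose.

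- T = 11, r_I = 0.3: (0.6 + 1.8)/11 = 0.218, which is +9%.
- T = 11, r_I = 0.5: (1.0 + 1.8)/11 = 0.255, which is +27%.
- T = 12, r_I = 0.3: (0.6 + 2.0)/12 = 0.217, which is +8%.
- T = 12, r_I = 0.5: (1.0 + 2.0)/12 = 0.250, which is +25%.

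The range is +8% to +27%.

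**Step 3: by-course ARR ratio, true value 1.00.** With i the DAT inflation from step 2, the ratio is (1 + 0.5·i)/(1 + 0.3·i). At T = 11:

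- i = 0.091: 1.0455/1.0273 = 1.02.
- i = 0.273: 1.1364/1.0818 = 1.05.

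With equal DAT shares the ratio is 1.00, but both ARRs are still too high.

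**Step 4: Kaplan-Meier gap, true value 0.** The gap is (0.5 − 0.3) × (DAT failed − IAT failed). For IAT the proportion failed is 1 − exp(−0.2t). For DAT it is 1 − exp(−2·r_I − 0.2(t − 2)) from year 2 on.

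| | IAT failed | DAT failed, r_I = 0.3 | DAT failed, r_I = 0.5 | Gap (points) |
|---|---|---|---|---|
| Year 2 | 33.0% | 45.1% | 63.2% | 2.4 to 6.0 |
| Year 11 | 88.9% | 90.9% | 93.9% | 0.4 to 1.0 |

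**Step 5: EDSS and MRI.** SAP 2.4.4 uses TOPAZ assessments plus the earlier baseline, so interferon-period assessments are not outcomes themselves. Each change from the long-term baseline in a DAT patient nevertheless includes the net change during interferon. This applies to EDSS change, to lesion-volume and BPF change, and to the descriptive change in lesion counts. Cumulative lesion counts run from TOPAZ D1 (2.1.3.3.1), so there the pre-interferon value enters only as a covariate. The documents give nothing from which to size these effects.

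**The case against.** **The SAP follows the protocol.** Protocol 9.2 sets baseline at inclusion in the initial studies, and 11.4.1 assesses former interferon patients from their first study treatment. This stands for the general long-term evaluation and for IAT versus DAT, where the early start is the point of the comparison. Neither section mentions a split by course, which appears only in the SAP, so neither justifies that origin for it.

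**The models may adjust.** The IAT/DAT indicator is in the ARR, Cox and EDSS models, prior study is in the ARR and Cox models, and ARR is also shown by year. If the by-course versions keep these terms, the modelled contrast is partly protected. The SAP does not say whether they do, and observed ARRs and Kaplan-Meier curves are unadjusted in any case.

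**The stakes are limited.** "The primary objective is to evaluate long-term safety of alemtuzumab". Efficacy is secondary, the study is non-comparative, the protocol plans no formal hypothesis tests, and the by-course results are an addition to the main comparison. All of this stands and limits the weight of the point.

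**Stronger readings that the documents do not support**

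- A reader might take the difference in patients who fail before alemtuzumab, 0.2 × (45% to 63%) = 9 to 13 points, as the distortion of the curves. It is not, because IAT patients also relapse in years 1 and 2 (33% at the assumed rate).
- A reader might infer that interferon time falls mainly on the ≤3 group, because DAT patients had about 2 fewer years to accumulate courses given at least 12 months apart. That is plausible, but no passage gives the DAT share by course group, and further courses depended on disease activity.
- A reader might infer that restarting the clock yields a fair comparison of few and many courses. It does not: course number is settled after baseline, by disease activity.

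**Conclusion.** The point holds on the text. The by-course summaries share an origin that is right for IAT versus DAT and does not fit a grouping by alemtuzumab courses. What the documents establish is that about 2 of some 11 to 12.5 DAT years (16-18%) are interferon time counted under a course heading.

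The effect on results depends on the assumed rates and shares. DAT ARR is 8-27% too high; the ARR ratio between course groups is about 1.02-1.05 where 1.00 is true; and the Kaplan-Meier gap is about 2-6 points at year 2, fading to 1 point or less by year 11. With equal DAT shares there is no spurious contrast, but both groups' results still include interferon time. This is a modest flaw in a secondary, descriptive analysis. It should be corrected because the tables would not report what their heading says.

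**What to change.** In SAP 2.4.4 and 2.4.4.1.1 to 2.4.4.1.5:

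- Start every by-course analysis at first alemtuzumab dose: in the core study for IAT, in CAMMS03409 for DAT. Exclude interferon-period relapses and follow-up.
- Use the last EDSS or MRI before that dose as baseline where available. The documents do not say that these assessments are held for DAT patients. Where they are not, present by-course EDSS and MRI separately for IAT and DAT, and label the DAT results as including interferon time.
- Keep the core-study start for IAT versus DAT, as in protocol 9.2 and 11.4.1.
- Record the by-course start in SAP 1.5, which now lists no modification, and add the matching exception to the reference date in 2.5.1.
- State that course number is determined after baseline by disease activity, so the by-course contrast remains descriptive.

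The cost is SAP wording and a different start date for DAT patients in the by-course programs. No new relapse data are needed: SAP 2.1.1 already derives time since first alemtuzumab infusion, and 2.4.4 already obtains CAMMS03409 relapse data. The downside is about 2 years less DAT follow-up in these tables.

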##### **2.4.4.1 Analysis of efficacy endpoint(s)**

###### **2.4.4.1.1 Annualized relapse rate (ARR)**

The estimated annualized relapse rate using negative binomial model with robust variance estimation will be presented by year and in overall. The observed total number of relapses is the dependent variable, the log total amount of follow-up time in years for each patient will be the offset variable and analysis group indicator (IAT vs DAT) and geographic region will be the covariates in the model. Both IAT vs DAT comparison and ARR by alemtuzumab courses will be analyzed. The analysis period starts from prior studies (CAMMS323/324) until the end of TOPAZ study. The model will also be stratified by previous clinical study.

The observed annualized relapse rate will be reported as well, which is defined as the total number of relapses divided by the total years of follow-up for each patient.

The ARR will be presented separately for retreated population in overall group.

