### **5.2 SECONDARY**

The secondary objectives are:

- To evaluate long term efficacy of alemtuzumab.
- To evaluate the safety profile of patients who received other DMT following alemtuzumab treatment.
- To evaluate patient-reported quality of life (QoL) outcomes and health resource utilization of patients who received alemtuzumab.
- To evaluate as needed re-treatment with alemtuzumab and other DMTs.

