#### **2.3.1.1 Retreated population**

The population is defined as safety patients who have received study drug in TOPAZ study.

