#### *2.4.4.1.3 EDSS*

The observed value, change from baseline as well as percentage change from baseline will be presented descriptively. The change from baseline in EDSS will be analyzed using a mixed model for repeated measures (MMRM) (7)(8)(9) with baseline EDSS score, analysis group indicator (IAT and DAT), geographic region, study visit and study visit by analysis group interaction as covariates. The TOPAZ study baseline at study entry is considered as post-baseline for efficacy analysis. The comparison of the change from baseline in EDSS with the MMRM will include the change from baseline to each consecutive year which can be constructed using the linear contrasts of the estimated regression parameters. All post-baseline EDSS scores will be included in the MMRM; patients without any post-baseline scores will not be included. For this model, imputation will not be used.

Similar analysis for change of EDSS by alemtuzumab courses and for retreated population will be analyzed as well.

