#### **2.4.5.3 Analyses of laboratory variables**

Laboratory analysis will be conducted for retreated population and 48 months follow-up population. The baselines for each population are defined as below.

- Retreated population baseline: The last non-missing assessment prior to first dose of alemtuzumab in TOPAZ study. The baseline should be taken within 2 weeks prior to the treatment for laboratory assessment except for HPV and pregnancy test. For HPV and pregnancy test, it can be taken in 12 months before the treatment.
- 48 months follow-up population baseline: The last non-missing assessment prior to the last dose of alemtuzumab in previous studies. The baseline should be taken within 2 weeks

prior to the treatment for laboratory assessment except for HPV and pregnancy test. For HPV and pregnancy test, it can be taken in 12 months before the treatment.

The summary statistics (including number, mean, median, Q1, Q3, standard deviation, minimum and maximum) of all laboratory variables (central laboratory values and changes from baseline) will be calculated for each visit or study assessment (baseline, each postbaseline time point, last on-treatment and/or worst on-treatment value and/or other specific assessment) in overall group and by subgroups (IAT vs DAT). This section will be organized by biological function [Section 2.1.4.3](#).

The incidence of PCSAs (list provided in [Appendix A](#)) at any time during the treatment-emergent adverse event period will be summarized by biological function and in overall group and by subgroups (IAT vs DAT) whatever the baseline level and/or according to the following baseline status categories:

- Normal/missing
- Abnormal according to PCSA criterion or criteria

For parameters for which no PCSA criteria are defined, similar table(s) using the normal range will be provided.

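### Relapse summaries for the retreated population inherit a period that starts in the core studies, so the efficacy part of the re-treatment objective has no output anchored at the TOPAZ infusion

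*SAP*

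**What the plan says.** One secondary objective in Protocol 5.2, repeated in SAP 1.2.2, is "To evaluate as needed re-treatment with alemtuzumab and other DMTs".

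SAP 2.3.1.1 defines the retreated population by an event inside TOPAZ: "The population is defined as safety patients who have received study drug in TOPAZ study".

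The efficacy sections treat this group as follows:

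- **ARR (SAP 2.4.4.1.1).** The main analysis period is given as "The analysis period starts from prior studies (CAMMS323/324) until the end of TOPAZ study". The closing line is "The ARR will be presented separately for retreated population in overall group", with no period of its own.
- **Relapse-free proportion (SAP 2.4.4.1.2).** The same period is stated, followed by "The Kaplan-Meier (KM) estimates will be summarized for retreated population separately".
- **EDSS (SAP 2.4.4.1.3).** Baseline is the core-study value: "The TOPAZ study baseline at study entry is considered as post-baseline for efficacy analysis". Then: "Similar analysis for change of EDSS by alemtuzumab courses and for retreated population will be analyzed as well".
- **MRI (SAP 2.4.4.1.4 and 2.4.4.1.5).** A similar analysis is promised for retreated patients, again with no baseline specific to them.

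The general reference dates are the first core-study treatment (SAP 2.5.1) and TOPAZ D1 for efficacy visit windows (SAP 2.5.3.2). Neither is the infusion.

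SAP 2.4.5.3 does set an infusion-specific baseline for laboratory data: "Retreated population baseline: The last non-missing assessment prior to first dose of alemtuzumab in TOPAZ study". SAP 2.4.5.4 does the same for infusion vital signs, using the value before the steroid.

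**The concern.** A group defined by an infusion in TOPAZ is summarised over a period that begins years before that infusion. Re-treatment is at the investigator's discretion, and Protocol 6.1 and 10.1.5 ask for the clinical or imaging reasons to be documented. Some relapses that prompt re-treatment will therefore be counted in the result reported for the retreated group.

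Two consequences follow. An effect of the new course on relapse is diluted in the ARR. And for anyone re-treated after a relapse, time to first relapse ended before the infusion, so the curve holds nothing about what came after it. What is at stake is whether the study can describe disease activity after as-needed re-treatment.

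**Working it through.** The plan states no sample size, event count or expected rate for this analysis, so there is no figure to reproduce. The check is person-time arithmetic, followed by illustrations that need assumed relapse rates.

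**Inputs.** Core study 2 years and extension at least 4 years (SAP 1.4); extension up to 60 months (Protocol 4); TOPAZ 5 years plus a 6-month window (SAP 1.1). The infusion date is not scheduled (Protocol 8.1.1), so let t be the years from D1 to the first TOPAZ infusion.

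**Step 1: share of relapse follow-up before infusion.** Share = (core + extension + t) / (core + extension + TOPAZ).

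| t (years) | 2 + 4 + 5 years | Range: extension 4–5, TOPAZ 5–5.5 |
|---|---|---|
| 0 | 6/11 = 54.5% | 52.2% (6/11.5) to 58.3% (7/12) |
| 2.5 | 8.5/11 = 77.3% | 73.9% to 79.2% |
| 4 | 10/11 = 90.9% | 87.0% to 91.7% |

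The minimum, 52%, needs an infusion on D1 itself and the longest TOPAZ follow-up. Shorter TOPAZ follow-up raises it: 6/10 = 60% with 4 years and 6/9 = 67% with 3 years, both at t = 0. No relapse rate is assumed here. Presenting ARR by year does not separate the two phases, because the years count from the core study and infusion dates vary.

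**Step 2: dilution of the ARR.** Assume a constant rate before infusion, multiplied by r afterwards, over 11 years. Whole-period ratio against no effect = [(6 + t) + r(5 − t)] / 11. With r = 0.5:

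- t = 1: (7 + 2)/11 = 0.82
- t = 2.5: (8.5 + 1.25)/11 = 0.89
- t = 4: (10 + 0.5)/11 = 0.95

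A true halving appears as a fall of 18%, 11% or 5%.

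**Step 3: Kaplan-Meier.** Probability of a first relapse before infusion = 1 − exp[−rate × (6 + t)]. At t = 2.5 and assumed rates of 0.2, 0.4 and 0.6 per year, this is 82%, 97% and 99%. For a patient re-treated because of a relapse it is 100% by construction.

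**Step 4: relapse-triggered scenario.** Simulation assuming 11 years, relapse rates gamma-distributed between patients (mean 0.15, shape 1) and re-treatment in the month after the first TOPAZ relapse. Post-infusion time is 27% of the total.

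| True effect after infusion | Whole-period ARR | Post-infusion ARR |
|---|---|---|
| None | 0.290 | 0.255 |
| Halved | 0.255 | 0.131 |
| Abolished | 0.221 | 0 |

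Complete abolition shows as 1 − 0.221/0.290 = 24%. Across shapes 0.5 to 2 and means up to 0.25 the figure is 21% to 28%.

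**Step 5: EDSS and MRI.** Under SAP 2.4.4, post-baseline data come from TOPAZ only, so the share of those data before infusion is t/5: 20% at t = 1, 50% at t = 2.5, 80% at t = 4. Cumulative lesion counts start at D1 (SAP 2.1.3.3.1). A change from the long-term baseline still spans at least 2 + 4 = 6 years before the infusion.

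**The case against.** **The origin is inferred.** The lines on retreated patients only say that results are shown separately. The core-study start is inherited from the section and is not restated for this group. It also does not fit everyone: the efficacy population includes CAMMS223 patients (SAP 2.3.2), yet the relapse period and the relapse data sources in SAP 2.4.4 omit that study. This stands, and it is why the point is worded as inherited. It does not remove the gap, since no other origin is offered.

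**Not all efficacy is mainly pre-infusion.** A reader might infer that every efficacy result for this group chiefly describes the years before re-treatment. The documents do not support that. Cumulative lesion counts start at D1, lesion volume and BPF are also reported year to year (SAP 2.4.4.1.5), and post-baseline EDSS and MRI data are from TOPAZ. The majority-before-infusion result holds for the relapse endpoints only.

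**The objective is not left wholly unanswered.** That reading is also too strong. The plan reports the percentage re-treated and time to treatment (Protocol 11.2), other MS therapies (SAP 2.4.2), number of courses (SAP 2.4.3.1), temporally associated AESIs and infusion reactions (SAP 2.4.5.1), and laboratory and vital-sign results with infusion baselines.

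**No biased comparison with other patients is planned.** The main contrast is IAT versus DAT (SAP 2.4.4). No efficacy contrast of retreated with non-retreated patients is specified.

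**An infusion-anchored analysis has its own bias.** This stands. In the Step 4 model with no treatment effect, ARR is 1.04 in the 12 months before infusion and about 0.25 after it, a spurious fall of 76% (67% to 80% for shapes 0.5 to 2). Against the whole pre-infusion period the artefact is smaller: pre-infusion ARR = (0.290 − 0.27 × 0.255)/0.73 = 0.30, a fall of about 16%. Post-infusion ARR with no effect also stays above the assumed cohort mean (0.255 against 0.15), because the group is selected.

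**Conclusion.** The point holds for the relapse endpoints. As written, the retreated ARR and relapse-free curve cover a period of which at least 52% precedes the infusion (about 77% at 2.5 years, 91% at 4 years). That rests only on the stated study durations and on the section's period applying to this group. The dilution and Kaplan-Meier percentages also rest on assumed relapse rates, and the 24% figure on every re-treatment following a relapse. Imaging-triggered re-treatment of patients with no earlier relapse is an exception to the Kaplan-Meier argument.

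For EDSS and MRI the point is narrower: visits before and after infusion are mixed, and no change is measured from the infusion. The efficacy part of the re-treatment objective therefore lacks an infusion-anchored output. The whole-period results are not an error, since Protocol 9.2 and 11.4.1 call for efficacy from the core-study baseline. The remedy is an addition, and it should be made.

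**What to change.** - **SAP 2.4.4.1.1 and 2.4.4.1.2:** for the retreated population, add an analysis with time zero at the first TOPAZ infusion, reporting ARR after infusion and Kaplan-Meier time from infusion to next relapse. This also gives retreated CAMMS223 patients a defined origin.
- **SAP 2.4.4.1.3 to 2.4.4.1.5:** add EDSS and MRI change from the last assessment before that infusion, mirroring the baseline principle in SAP 2.4.5.3.
- **Whole-period results:** keep them as long-term context, and state their time origin for this group.
- **Interpretation:** label the post-infusion results descriptive. If pre-infusion ARR is shown, use the longer pre-infusion period as the main reference. State that relapse-triggered re-treatment inflates the 12 months before infusion, so a fall from that window is regression to the mean and not evidence of effect.

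The cost is SAP wording and programming; infusion dates, relapses, EDSS and MRI are already collected. Follow-up shrinks to about 5 − t years (2.5 years for an infusion at 2.5 years, 1 year for one at 4 years), so intervals will be wider. The IAT versus DAT analysis is unchanged.
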